6.2.4.3. Binary Endpoints

- Endpoints:
 - Weeks 2, 4, 8 and 12 Response based on Achieving ≥ 2.5 -point Improvement from Baseline in the CDLQI Score;
 - Weeks 2, 4, 8 and 12 Response based on the PtGA of clear (0) or almost clear (1) (on a 5 point scale) and a reduction from baseline of ≥ 2 points at all scheduled time points.
- Estimand strategy: Composite, Estimand 1(Section 2.1.1).
- Analysis set: FAS (Section 4). Participants must have baseline CDLQI ≥ 2.5 to be included in the analysis of CDLQI. Participants must have baseline PtGA ≥ 2 to be included in the analysis of PtGA.
- Analysis methodology: CMH and normal approximation in Section 5.2.1.
- Intercurrent events and missing data: The intercurrent event is captured through the variable definition; for participants who drop out for any reason, the response will be defined as “non-responsive” after that point.
- The number of participants, number and percent of response at each specified timepoints along with the 95% confidence interval by normal approximation will be presented for each treatment arm.

- The CMH test p-value, the estimate of the difference in proportions of response at each specified timepoints along with the corresponding 95% confidence interval by CMH normal approximation will be presented for each PF-04965842 dose group versus placebo.

6.3. Other Endpoint(s)

6.3.1. Immunogenicity Sub-Study

- Endpoints:
 - Fold Increase from Baseline in Concentrations of IgG Against Tetanus Toxoid, Diphtheria Toxoid, Pertussis Toxoid, Pertactin (PRN), Filamentous Hemagglutinin (FHA), and Fimbriae Types 2 and 3 (FIM) at 4 Weeks Post vaccination.
- Analysis set: Immunogenicity sub-study Analysis Set (Section 4).
- Analysis methodology: CI using the Student's t distribution in Section 5.2.2 for the geometric mean fold rise (GMFR).
- Intercurrent events and missing data: Only observed data will be used.
- The number, median, first and third quartiles, minimum, maximum for the fold increase will be presented for each treatment arm.
- GMFR and the responding 95% CI will be presented for each treatment arm.
- GMFR ratio and the responding 95% CI between treatment groups for each PF-04965842 dose group versus placebo will also be presented.

CCI

[Redacted]

[Redacted]

[Redacted]

[Redacted]

[Redacted]

[Redacted]

[Redacted]

[Redacted]

[Redacted]

[Redacted]

090177e19618b8f5\Approved\Approved On: 25-Jan-2021 08:47 (GMT)

CC
I [REDACTED]

CCI [REDACTED]

I [REDACTED]

I [REDACTED]

I [REDACTED]

I [REDACTED]

I [REDACTED]

I [REDACTED]

I [REDACTED]

6.4. Subset Analyses

Summary statistics for co-primary endpoints will be presented by subgroups below.

- Age (years) group (less than or equal to the median value in FAS, above the median value);
- Sex (Male, Female);
- Race (White, Black or African-American, Asian, Other¹);
- Region of enrollment (US/Canada/Australia, Latin America, Europe, Asia);
- AD Duration (years) group (less than or equal to the median value in FAS, above the median value);

¹ For purposes of analysis, other will comprise the categories of American Indian or Alaska Native, Native Hawaiian or Other Pacific Islander, Multi-Racial and any other category reported on the CRF.

- Baseline disease severity (moderate, severe);
- Baseline EASI group (16-25, >25);
- Baseline % BSA group (10-30, >30-50, >50);
- Previous use of systemic immunosuppressant for AD (Yes, No).

Estimates of the difference between the active dose groups and placebo, along with the 95% confidence interval (no p-value) will be presented for each defined category of each subgroup. For the binary endpoints, analyses will be performed using normal approximation without any adjustments for baseline disease severity.

The primary purpose of the subgroup analyses is to check for consistency of results across subgroups, to make sure overall results are not being driven by some subset of participants.

Graphical display (eg, forest plots) of the differences between treatment groups will be presented, along with the Total difference. There is no intention to have any specific inference within subgroups.

6.5. Baseline and Other Summaries and Analyses

6.5.1. Baseline Summaries

Demographics and medical history including variables defined in Section 3.4 will be summarized by treatment group according to Pfizer standards.

6.5.2. Study Conduct and Participant Disposition

Participants evaluation, disposition, discontinuation will be summarized according to Pfizer standards.

6.5.3. Study Treatment Exposure

- Duration of Treatment is defined as the total number of dosing days on which study drug was actually administered; if N total doses missed on unknown dates, it reduces the Duration of Treatment by N/2 (when N is an event number) or (N-1)/2 (when N is an odd number);
- Exposure Time is defined as the total number of days from first to and including last day of study oral dosing (Last Oral Dosing Date - First Oral Dosing Date + 1);
- Dose Compliance is defined as the number of doses of study drug the subject took out of the expected total number of doses of study drug.
 - Expected Number of Doses = 2*(Exposure Time)
 - Dose Compliance = (Total Actual Oral Pills/ Expected Number of Doses) * 100%

Number, mean, standard deviation, median, minimum and maximum will be presented for those variables: Duration of Treatment, Exposure Time and Dose Compliance. Number and percent will be reported for subjects in Duration of Treatment categories, and Dose Compliance <80% and Dose Compliance >120%.

6.5.4. Concomitant Medications and Nondrug Treatments

Prior drug and non-drug treatment, concomitant drug and non-drug treatment will be summarized according to CaPS.

6.5.4.1. Background Topical Therapy (Medicated and Non-Medicated)

Number and percent of subjects used non-medicated emollient, medicated topical therapy, topical corticosteroids (TCS), topical calcineurin inhibitors (TCI), topical PDE4 inhibitors will be reported during the study treatment exposure period.

Subjects must comply with standardized background topical therapy guidance throughout the study (Protocol Section 6.5.2). “Did the subject conform to background therapy per protocol” is ‘No’ when medication should have been used per protocol and was not used OR if medication was used but did not meet protocol requirements.

- Exposure Time (of study treatment) is defined as the total number of days from first to and including last day of study dosing (Last Dosing Date - First Dosing Date + 1);
- During the period of first dosing date to last dosing date, if any use of TCS, TCI or PDE4 inhibitor is non-compliance with protocol (ie, “No” is entered for “Did the subject conform to background therapy per protocol”), the compliance for that day is “No”;
- Medicated Topical Therapy Compliance = $1 - (\text{Days non-compliant with background topical} / \text{Exposure Time}) * 100\%$.

Number, mean, standard deviation, median, minimum and maximum will be presented for Medicated Topical Therapy Compliance. Number and percent will be reported for subjects with compliance of medicated topical therapy <80% and ≥80%.

6.6. Safety Summaries and Analyses

Safety analysis will be based on the SAF analysis set.

All clinical AEs, SAEs, treatment-emergent signs and symptoms (TEAEs), withdrawal due to AEs, ECGs, vital signs and safety laboratory data will be reviewed and summarized on an ongoing basis during the study to evaluate the safety of participants.

Safety data will be presented in tabular and/or graphical format and summarized descriptively, where appropriate. All safety endpoints will be listed and summarized in accordance with CaPS. Categorical outcomes (eg, AEs) will be summarized by participant counts and percentage. Continuous outcome (eg, blood pressure, pulse rate, etc.) will be summarized using N, mean, median, standard deviation, etc. Change from baseline in

laboratory data, ECGs, physical exams and vital signs will also be summarized. Participant listings will be produced for these safety endpoints accordingly.

Separate safety summaries will also be presented for the immunogenicity subgroup.

6.6.1. Adverse Events

The safety data will be summarized in accordance with CaPS. All safety data will be summarized descriptively through appropriate data tabulations, descriptive statistics, categorical summaries, and graphical presentations. Safety endpoints for the study include:

- Treatment-emergent AEs and SAEs;
- Withdrawals from active treatment due to AEs;
- Serious infections, defined as any infection (viral, bacterial, and fungal) requiring hospitalization or parenteral antimicrobials.

Treatment-emergent AEs will also be analyzed using a 3-tier approach. Risk differences between the active treatments and placebo will be used to summarize the results.

For Tier-1 events, point estimates, 95% confidence intervals and p-values will be presented graphically comparing each active dose group with placebo. No multiplicity adjustments will be made. For Tier-2 events, only point estimates and 95% confidence intervals will be presented graphically (see Section 5.2.6). Tier-3 events will be summarized as part of the overall AE summaries; AEs will be displayed by MedDRA system organ class (SOC).

It should be recognized that most studies are not designed to reliably demonstrate a causal relationship between the use of a pharmaceutical product and an adverse event or a group of adverse events. Except for selected events in unique situations, studies do not employ formal adjudication procedures for event classification. ^{CCI}

Adverse events start on or after day of Tdap vaccines will also be reported for participants in the sub-study.

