9.4.3. Safety Analyses

All safety analyses will be performed on the Safety Population. The safety data will be summarized in accordance with Pfizer Data Standards. All safety data will be summarized descriptively through appropriate data tabulations, descriptive statistics, categorical summaries, and graphical presentations. Safety endpoints for the study include:

- Treatment-emergent AEs and SAEs;
- Withdrawals from active treatment due to AEs;
- Serious infections, defined as any infection (viral, bacterial, and fungal) requiring hospitalization or parenteral antimicrobials or met other criteria that required the event be classified as serious;
- Safety laboratory tests (eg, hematology [including coagulation panel], chemistry and lipid profiles);
- Vital signs;
- ECG parameters if applicable.

Change from baseline on laboratory data and vital signs will be additionally summarized.

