10.3.2. Definition of SAE

If an event is not an AE per definition above, then it cannot be an SAE even if serious conditions are met (eg, hospitalization for signs/symptoms of the disease under study, death due to progression of disease).

An SAE is defined as any untoward medical occurrence that, at any dose:
a. Results in death
b. Is life-threatening The term 'life-threatening' in the definition of 'serious' refers to an event in which the participant was at risk of death at the time of the event. It does not refer to an event, which hypothetically might have caused death, if it were more severe.
c. Requires inpatient hospitalization or prolongation of existing hospitalization In general, hospitalization signifies that the participant has been detained (usually involving at least an overnight stay) at the hospital or emergency ward for observation and/or treatment that would not have been appropriate in the physician's office or outpatient setting. Complications that occur during hospitalization are AEs. If a complication prolongs hospitalization or fulfills any other serious criteria, the event is serious. When in doubt as to whether "hospitalization" occurred or was necessary, the AE should be considered serious. Hospitalization for elective treatment of a pre-existing condition that did not worsen from baseline is not considered an AE.
d. Results in persistent disability/incapacity 
 • The term disability means a substantial disruption of a person's ability to conduct normal life functions. • This definition is not intended to include experiences of relatively minor medical significance such as uncomplicated headache, nausea, vomiting, diarrhea, influenza, and accidental trauma (eg, sprained ankle) which may interfere with or prevent everyday life functions but do not constitute a substantial disruption.
e. Is a congenital anomaly/birth defect
f. Other situations: 
 • Medical or scientific judgment should be exercised in deciding whether SAE

090177e19618b8f7\Approved\Approved On: 25-Jan-2021 08:51 (GMT)

reporting is appropriate in other situations such as important medical events that may not be immediately life-threatening or result in death or hospitalization but may jeopardize the participant or may require medical or surgical intervention to prevent one of the other outcomes listed in the above definition. These events should usually be considered serious.

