10.5. Appendix 5: Monitoring and Discontinuation Criteria

Monitoring Criteria

The following laboratory abnormalities require prompt retesting:

- Neutrophil counts <1000 neutrophils/mm³; confirmed promptly by repeat testing, ideally within 3-5 days;
- Platelet counts $<75,000$ platelets/mm³; confirmed promptly by repeat testing, ideally within 3-5 days;
- Any single hemoglobin value <9.0 g/dL or one that drops ≥ 2 g/dL below baseline; confirmed promptly by repeat testing, ideally within 3-5 days;
- Any single AST and/or ALT elevation >3 times the upper limit of normal regardless of accompanying symptoms or the total bilirubin should prompt repeat testing. This should also prompt review of Appendix 6 (Liver Safety); additional investigations must be conducted.

Temporary Interruption to Dosing

Temporary interruption to dosing is not allowed in this study, except when indicated for participant safety. Sponsor clinician must be informed when temporary interruption occurs and the duration of temporary interruption must not exceed 14 days.

Discontinuation Criteria

Participants must be permanently discontinued from treatment if they meet any of the following criteria at any point in the study:

- Marked prolongation of the QTcF interval to >500 ms or >60 ms change from screening ECG.
- Serious infection (see definition for Serious Adverse Events in Section 10.3.2).
- Any bleeding event thought to be associated with a platelet count reduction per the judgement of the investigator (or, if necessary/desired, following discussion with sponsor).
- Adverse event, per judgment of the investigator, requiring discontinuation from treatment (or, if necessary/desired, following discussion with sponsor).
- Confirmed pregnancy (as described in Section 8.2.10)

NOTE: any initial lab value below must be retested within 48 hours.

- Two sequential platelet counts $<50,000/\text{mm}^3$. If the subject has a platelet count $<25,000/\text{mm}^3$, study intervention should be temporarily withheld pending the confirmatory retest.
- Two sequential neutrophil counts $<500/\text{mm}^3$.
- Two sequential lymphocyte counts $<500/\text{mm}^3$.
- Two sequential hemoglobin assessments $<8.0 \text{ g/dL}$ and / or a decrease of $> 30\%$ from baseline value.
- Any of the following:
 - Two sequential AST or ALT elevations >3 times the upper limit of normal with at least one total bilirubin value >2 times the upper limit of normal.

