1. VERSION HISTORY

Table 1. Summary of Changes

Version/ Date	Associated Protocol Amendment	Rationale	Specific Changes
1 19 Oct 2018	Original 13 Sep 2018	N/A	N/A
2	Protocol Amendment 4 26 Aug 2019	Modifications and clarifications of planned analyses to align with across the program. Deleted endpoints not used for CSR purpose, and added endpoints of interest.	
 • Added Percent change from baseline analysis in BSA, EASI, SCORAD total score, SCORAD subjective assessment of sleep loss, Peak Pruritus NRS; analysis for steroid free days in Section 2, Section 3.2.2 and Section 6.2. • Added responder analysis based CDLQI in Section 2, Section 3.3.1 and Section 6.2. • Deleted change from baseline analysis in SCORAD subjective assessment of itch in Section 2, Section 3.2.2 and Section 6.2. • Deleted PK endpoint in Section 2. • Deleted Hypothetical Estimand and analysis based on Hypothetical Estimand in Section 2.1.3, Section 6.1.1 and Section 6.1.2. • Deleted response based on CDLQI, HADS and POEM in Section 3.3.1 and Section 6.2. • Updated the definition of baseline variables in Section 3.4. • Updated the definition of a treatment emergent adverse event (TEAE) in Section 3.5.1, in alignment with the latest CaPS algorithm. • Updated the criteria for inclusion into the PPAS in Section 4. • Updated the analyses for Tier-1 Events in Section 5.2.6.

090177e19618b8f5\Approved\Approved On: 25-Jan-2021 08:47 (GMT)

			
 Updated method to manage missing data for binary endpoints. See sections 5.3.1 and Appendix 3. Updated study treatment exposure definitions and summaries in Section 6.5.3. Updated concomitant/background medications and non-drug treatment summaries in Section 6.5.4. Additional minor changes to improve clarity and alignment with the protocol.
--	--	--	---

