2. INTRODUCTION

This statistical analysis plan (SAP) provides the detailed methodology for summary and statistical analyses of the data collected in Study B7451036. This document may modify the plans outlined in the protocol; however, any major modifications of the primary endpoint definition or its analysis will also be reflected in a protocol amendment.

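### SAP 6.6.1 omits one of the protocol's three routes to a serious infection, so the descriptive count can fall below the protocol-defined count

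*SAP*

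**What the plan says.** Both documents put serious infections in a bulleted list introduced by the same words, "Safety endpoints for the study include", in Protocol 9.4.3 and SAP 6.6.1.

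- **SAP 6.6.1:** "Serious infections, defined as any infection (viral, bacterial, and fungal) requiring hospitalization or parenteral antimicrobials". The bullet ends at that point.
- **Protocol 9.4.3:** the same two conditions, followed by a third alternative, "or met other criteria that required the event be classified as serious".
- **Protocol Appendix 5 (Discontinuation Criteria):** lists "Serious infection (see definition for Serious Adverse Events in Section 10.3.2" as a ground for permanent discontinuation of treatment, and so ties the term to the full SAE definition.
- **Protocol 10.3.2:** besides hospitalization, the grounds for an SAE are death, threat to life, persistent disability, congenital anomaly and "important medical events that may not be immediately life-threatening or result in death or hospitalization".

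The SAP's version history has no entry on serious infection. Its closing catch-all reads "Additional minor changes to improve clarity and alignment with the protocol".

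**The concern.** A descriptive incidence is only as good as its case definition. The SAP reproduces the protocol bullet almost word for word but without the last alternative. An infection that is serious only on another ground, such as an important medical event managed without admission or parenteral treatment, meets the protocol definition and fails the SAP definition. Read literally, the SAP would also leave out a fatal or life-threatening infection in someone neither admitted nor given parenteral antimicrobials.

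Protocol 2.3 names serious infections among the potential risks of treatment, so readers of the study report will look for this count. Two things are at stake: whether it matches the protocol's definition, and whether it can be reconciled with discontinuations recorded as due to serious infection.

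**Working it through.** There is no planned figure to reproduce. The check compares three definitions.

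**Notation.** For an infection, let H = requires hospitalization, P = requires parenteral antimicrobials, O = serious on some other ground.

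- Protocol 9.4.3: H or P or O
- SAP 6.6.1: H or P
- Protocol Appendix 5, through 10.3.2: H or O. Parenteral treatment is not a listed SAE criterion.

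**Case by case:**

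| Infection | Protocol 9.4.3 | SAP 6.6.1 | Appendix 5 |
|---|---|---|---|
| Admitted | counted | counted | met |
| Parenteral treatment as outpatient, no SAE ground | counted | counted | not met |
| Parenteral treatment as outpatient, serious on another ground | counted | counted | met |
| Neither admitted nor parenteral, serious on another ground | counted | **not counted** | met |
| Neither admitted nor parenteral, not serious | not counted | not counted | not met |

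**Consequences.**

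1. Every infection in the SAP set is in the protocol set, so the SAP count is at most the protocol count. The difference is the fourth row: O without H and without P.
2. The fourth row meets the Appendix 5 criterion, so a participant can be discontinued for serious infection and be absent from the SAP count.
3. With the third clause restored, every infection that meets the Appendix 5 criterion (H or O) is in the count (H or P or O), and the gap in step 2 closes.

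**Scale.** The planned total is 225 in three equal arms, so 225/3 = 75 per arm. One missed participant is 1/75 = 0.0133, or 1.3 percentage points of that arm's incidence; k missed participants are k/75. The documents give no value for k in any arm. They therefore do not show how far a rate would move, nor in which direction a comparison with placebo would shift.

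**Could the gap have another explanation?** The SAP bullet is a complete statement, and the redaction mark in 6.6.1 comes in a later paragraph, so redaction does not account for it. The change log covers changes between SAP versions. Its silence shows that no reason was recorded, but not when the clause was lost.

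**The case against.** Four points can fairly be made for leaving the SAP alone.

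- **Nothing leaves safety reporting.** This stands. A reader might infer that the omitted infections go unreported, but an infection that qualifies only through the missing clause is an SAE. SAP 6.6.1 lists "Treatment-emergent AEs and SAEs" among the same bullets, displays AEs by system organ class and summarizes withdrawals due to AEs; SAP 6.6 adds participant listings. The SAE output does not replace the endpoint, though, because the protocol's definition also takes in infections given parenteral antimicrobials that meet no SAE ground. Neither output alone gives the protocol-defined count.
- **The SAP may depart from the protocol.** SAP Section 2 says "This document may modify the plans outlined in the protocol", and Protocol 9.4 agrees. An amendment is needed only for major changes to the co-primary endpoints or their analyses. So the narrower wording is permitted; the fault is that it is unexplained. A reader might infer a deliberate narrowing, but the documents give no evidence of intent.
- **The endpoint has modest standing.** It is absent from the endpoint lists in Protocol Section 3 and SAP 3.5, and has no hypothesis test of its own. That limits the weight of the point. Both analysis sections nevertheless call it a safety endpoint.
- **Protocol 9.4.3 and Appendix 5 already differ.** This is true of the second row of the table: outpatient parenteral treatment with no SAE ground is counted without meeting the discontinuation criterion. That is a case counted without a discontinuation. It does not undo the repair of the opposite gap, a discontinuation without a count.

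A reader might also infer that opportunistic infections and viral reactivation would be under-reported. The documents do not support that. Opportunistic infections, including eczema herpeticum, go to blinded Safety Adjudication Committees (Protocol 10.1.5). Suspected viral infection or reactivation has its own blood sampling (Protocol 8.2.8.3). Pre-specified events of clinical importance form Tier 1 (SAP 3.5.1), under a list held in a plan that is not part of these documents.

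**Conclusion.** The SAP definition is narrower than the protocol's, without explanation. Applied exactly, it can only match or undercount the protocol-defined number of serious infections, and it can omit a participant discontinued under Appendix 5 for that reason. The effect is confined to one descriptive safety count. SAE reporting, type I error and power are untouched.

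The only size the documents support is 1.3 percentage points of an arm's incidence per missed participant. This assumes the planned 75 per arm; the safety set, restricted to participants who took at least one dose, could be slightly smaller. With few events, one omission could be a large share of the total, and a reader might infer a large distortion. The documents give neither the expected number of serious infections nor the share that would qualify only through the missing clause, so no such figure can be stated. The conclusion rests on the wording of the two definitions and on the SAP bullet being applied as written. It should be corrected because the count concerns a named risk and the correction is trivial.

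**What to change.** In SAP 6.6.1, replace the serious-infection definition with the Protocol 9.4.3 wording, including the alternative for events classified as serious on other criteria, and record the change in the SAP version history. The cost is one line of text and the matching selection rule in the programming. No new data are needed, because Protocol 10.3.3 already requires all SAEs to be recorded on the CRF. The discontinuation criteria are not affected.
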